5.9.3. Analysis of Vital Signs

Vital signs (temperature, pulse, blood pressure, and respiration rate) will be listed and summarized by Baseline and change from Baseline to each scheduled assessment time with descriptive statistics.

5.9.4. Analysis of 12-Lead ECG

ECG parameters (PR interval, QT interval, QTc interval, QRS interval, Ventricular rate and Heart rate) will be listed and summarized by Baseline and change from Baseline to each scheduled assessment time with descriptive statistics.

ECG status (ie, normal, abnormal not clinically significant, and abnormal clinically significant) will be reported. Shift tables from baseline to worst post-baseline findings (normal, abnormal not clinically significant, and abnormal clinically significant) during on-treatment period will be generated.

5.9.5. Physical Exams

Physical examination findings at baseline as well as post-treatment abnormal findings by body system and status (normal, abnormal not clinically significant, and abnormal clinically significant) will be listed. Number and proportion of patients with new or worsened physical exam abnormalities during on-treatment period will be summarized.

5.10. Analysis of Pharmacokinetic and Immunogenicity Data

5.10.1. Analysis of Pharmacokinetic Data

Serum concentration of cemiplimab will be assessed at multiple time points throughout the study treatment and follow-up periods, and the PK variables will be determined.

Summaries of study drug concentrations will be presented by nominal time point (ie, the time points specified in the protocol) and group. Pharmacokinetic variables, including C_{eoi} , C_{trough} , and t_{eoi} , will be presented as individual values with descriptive statistics.

5.10.2. Analysis of Anti-Drug Antibody Data

The anti-drug antibody variables described in Section 4.7 will be summarized using descriptive statistics.

Immunogenicity will be characterized by ADA responses and titers observed in patients in the ADA analysis set. ADA response categories and titer categories are defined as follows:

ADA response categories:

- ADA Negative, defined as ADA negative response in the cemiplimab ADA assay at all time points, regardless of any missing samples.
- Pre-existing immunoreactivity, defined as either an ADA positive response in the ADA assay at baseline with all post first dose ADA results negative, OR a positive response at baseline with all post first dose ADA responses less than 9-fold over baseline titer levels.
- Treatment-emergent response, defined as a positive response in the ADA assay post first dose when baseline results are negative or missing. The treatment-emergent responses will be further characterized as Persistent, Indeterminate or Transient.
 - Persistent Response – Treatment-emergent ADA positive response with two or more consecutive ADA positive sampling time points, separated by at least 16-week period (based on nominal sampling time), with no ADA negative samples in between, regardless of any missing samples.
 - Indeterminate Response – Treatment-emergent ADA positive response with only the last collected sample positive in the ADA assay, regardless of any missing samples.
 - Transient Response – Treatment-emergent ADA positive response that is not considered persistent or indeterminate, regardless of any missing samples.
- Treatment-boosted response, defined as a positive response in the ADA assay post first dose that is greater than or equal to 9-fold over baseline titer levels, when baseline results are positive.

Titer categories (Maximum titer values):

- Low (titer <1,000)
- Moderate ($1,000 \leq \text{titer} \leq 10,000$)
- High (titer >10,000)

The following analysis will be provided:

- Number (n) and percent (%) of ADA-negative patients (pre-existing immunoreactivity or negative in the REGNXXXX ADA assay at all time points) by treatment groups
- Number (n) and percent (%) of treatment-emergent ADA positive patients by treatment groups and ADA titer categories

- Number (n) and percent (%) of persistent treatment-emergent ADA positive patients
- Number (n) and percent (%) of indeterminate treatment-emergent ADA positive patients
- Number (n) and percent (%) of transient treatment-emergent ADA positive patients
- Number (n) and percent (%) of treatment-boosted ADA positive patients by treatment groups and ADA titer categories
- Listing of all ADA titer levels will be provided for patients with pre-existing, treatment-emergent and treatment-boosted ADA response.

Formation of ADA will be assessed in individual patients and per group as follows:

- Possible relationship between changes in PK profile and treatment-emergent positive responses in the ADA assay will be assessed to evaluate a potential impact of anti cemiplimab antibodies on drug exposure.
- Possible relationship between AEs and treatment-emergent positive responses in the ADA assay will be assessed to evaluate a potential impact of anti-cemiplimab antibodies on the incidence of Grade 3 and 4 AEs, atypical AEs, and SAEs.

Cases of ADA positivity will be listed and summarized as appropriate. Analysis of ADA data will be provided in a separate report.

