^f. Vital signs include temperature, resting blood pressure, pulse, and respiration. Vital signs will be assessed and documented prior to the cemiplimab infusion, and then approximately 15 minutes after the completion of the cemiplimab infusion. The allowable window for each specified time point is ±10 minutes.

^g. Brain MRI with gadolinium is required at screening only if the investigator feels that there is clinical suspicion of brain metastases. Brain scans during the treatment and follow-up periods are required if there is a prior history of lesions present at screening or as clinically indicated. A brain CT with iodinated contrast may be performed if an MRI with gadolinium is contraindicated.

- h. Hematology includes: WBC count, 3-cell differential (ANC, monocyte count, lymphocyte count), hemoglobin, and platelet count. Samples may be collected ≤72 hours prior to study treatment.
- i. Chemistry includes: sodium, potassium, chloride, bicarbonate, calcium, magnesium, phosphorous, glucose, albumin, creatinine, blood urea nitrogen (BUN), ALT, AST, total bilirubin, alkaline phosphatase (ALP), uric acid, and LDH. Samples may be collected ≤72 hours prior to study treatment.
- j. Predose β-HCG (serum) at screening up to 72 hours prior to first administration. Subsequent predose pregnancy tests may be urine β-HCG. Serum pregnancy test and urine pregnancy test are requirements for WOCBP only.
- k. Urinalysis: glucose, blood, pH, specific gravity, ketones, and spot urine protein.
- l. ADA samples are collected prior to treatment on day 1 of cycles 1, 3, 5, 9 and at EOS (for patients who discontinue treatment due to progression or toxicity during cycles 1 through 12) or at the follow-up visit 1 in Table 94† (for patients who complete cycles 1 through 12).
- m. Blood samples for PK will be collected on cycle 1 day 1 at pre-infusion and end-of-infusion; on cycle 1 day 22 at pre-infusion; on cycle 3 day 1 at pre-infusion and end-of-infusion; on day 1 of cycles 5 and 9 at pre-infusion (see Appendix 3). The final PK sample will be collected either at the EOS visit (for patients who discontinue treatment due to progression or toxicity during cycles 1 through 12) or at the follow-up visits 1, 2, 3, 4 and 7 (for patients who complete cycles 1 through 12).

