9.5.6. Analysis of Anti-Drug Antibody Data

Formation of ADA will be assessed in individual patients and per treatment group as follows:

- Possible correlation between changes in PK profile and the presence/absence of anti-cemiplimab antibodies will be evaluated to identify a potential impact of anti-cemiplimab antibodies on drug exposure.
- Possible correlation between AEs and the presence/absence of anti-cemiplimab antibodies may be evaluated to identify a potential impact of anti-cemiplimab and/or antibodies on the incidence of Grade 3 and 4 AEs, atypical AEs, and SAEs.

Cases of ADA positivity will be listed and summarized as appropriate.

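### SAP 5.10.2 classes a treatment-emergent ADA response as transient when the positive run ends at the last collected sample but spans less than 16 weeks, although no later negative was seen.

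*SAP*

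**What the plan says.** SAP 5.10.2 divides treatment-emergent ADA responses into three classes.

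- Persistent requires "two or more consecutive ADA positive sampling time points, separated by at least 16-week period (based on nominal sampling time"), with no negative sample in between.
- Indeterminate is a "Treatment-emergent ADA positive response with only the last collected sample positive in the ADA assay, regardless of any missing samples".
- Transient is the residual class: "Treatment-emergent ADA positive response that is not considered persistent or indeterminate, regardless of any missing samples".

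Each class is a planned output; one of the listed tabulations is "Number (n) and percent (%) of transient treatment-emergent ADA positive patients". Protocol 8.3 defines only treatment-emergent, treatment-boosted and titer categories, so it does not override this split.

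For Group 6, the ADA note to protocol Table 7 states that "ADA samples are collected prior to treatment on day 1 of cycles 1, 3, 5, 9 and at EOS" for patients who stop because of progression or toxicity, or at follow-up visit 1 for those who complete 12 cycles. The same table places the end-of-study (EOS) visit 30 days after the last dose, with a window of 21 to 42 days.

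**The concern.** The three definitions do not order the evidence sensibly. One positive at the very end of sampling is Indeterminate, because nobody knows what happened next. Two consecutive positives at the end, less than 16 weeks apart, are stronger evidence that antibodies were still present, yet they are Transient. The class has no requirement for a later negative, and the wording makes no exception for sampling cut short by early discontinuation.

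Immunogenicity is a secondary objective (SAP 1.2.2). At stake is whether the reported split between Transient and Indeterminate means what a reader will take it to mean. The discrepancy also depends on when a patient left the study, so it is not spread evenly over patients.

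**Working it through.** The plan states no figure to reproduce beyond the 16-week threshold (112 days). The check applies the three definitions to the sampling schedule.

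**Inputs for Group 6**
- Cycle length 63 days, doses on days 1, 22 and 43, up to 12 cycles (SAP 2.3). Doses fall 0, 21 and 42 days after cycle start.
- Post-baseline ADA samples on day 1 of cycles 3, 5 and 9 (protocol Table 7): (3−1)×9 = week 18, (5−1)×9 = week 36, (9−1)×9 = week 72.
- EOS sample at last dose + 30 days (21 to 42).
- Reading used: a run is measured from its first to its last positive sample, and EOS is placed at its actual distance from the last dose.

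**Step 1, the logic.** Take a patient whose only positives are the last two samples, d days apart, with d < 112. Persistent fails because d is under 16 weeks. Indeterminate fails because the last sample is not the only positive. Transient follows by default.

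**Step 2, the gap.** Gap = (days from day 1 of the sampled cycle to the last dose) + (days from the last dose to EOS).

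| Last dose | Gap with EOS at 30 days | Range for EOS at 21 to 42 days | Class at 30 days |
|---|---|---|---|
| Sampled cycle, day 1 | 0 + 30 = 30 d = 4.3 wk | 3.0 to 6.0 wk | Transient |
| Sampled cycle, day 22 | 21 + 30 = 51 d = 7.3 wk | 6.0 to 9.0 wk | Transient |
| Sampled cycle, day 43 | 42 + 30 = 72 d = 10.3 wk | 9.0 to 12.0 wk | Transient |
| Next cycle, day 1 | 63 + 30 = 93 d = 13.3 wk | 12.0 to 15.0 wk | Transient |
| Next cycle, day 22 | 84 + 30 = 114 d = 16.3 wk | 15.0 to 18.0 wk | Persistent |

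The table applies after the cycle 3, 5 and 9 samples. After cycle 3, the affected patient can be positive at every post-dose sample taken. After cycles 5 and 9, the preceding sample must have been negative; otherwise the run already spans 18 or 36 weeks and is Persistent.

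From cycle 3 day 1 onward there are 12×3 − 6 = 30 possible last-dose visits. With EOS at 30 days, 4×3 = 12 of them give the pattern; at 21 days it is 5×3 = 15; at 42 days it is 12. These are counts of visits, not of patients.

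**Step 3, a typical case.** Tumor assessments come at the end of each cycle. A patient who progresses at the week 27 scan has a last dose at cycle 3 day 43 (week 24), EOS near week 28, and a gap of 10.3 weeks. Progression one cycle later gives 63 + 42 + 30 = 135 days = 19.3 weeks, which is Persistent if both samples are positive.

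**Step 4, completers.** Gaps between post-baseline on-treatment samples are 16 weeks (Groups 1, 2 and 4), 18 weeks (Groups 3 and 5), and 18 and 36 weeks (Group 6). From the last on-treatment sample to follow-up visit 1 the gap is 96+4−32 = 68 weeks (Groups 1 and 2), 54+4−36 = 22 (Groups 3 and 5), 48+4−32 = 20 (Group 4) and 108+4−72 = 40 (Group 6). None is under 16 weeks, so up to that visit completers do not meet the pattern.

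**Step 5, early stoppers in the other groups.** Protocol Tables 3 to 6 schedule no ADA sample at EOS, so progressors in Groups 1 to 5 have no such pair. Patients who stop for other reasons move to follow-up. If visit 1 is taken as last dose + 28 days (an assumption), the gap can be 4 to 14 weeks (Groups 1 and 2), 4 to 13 (Group 3) or 4 to 12 (Group 4). This matters only if the later visit 7 sample is never obtained.

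**The case against.** The strongest reply is that Transient is openly a residual class, that the SAP lists every titer for treatment-emergent patients so the true pattern stays visible, and that the affected set is narrow. All of that is true and limits the importance of the point. It does not repair the tabulated n (%), which will be read without the listing.

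A reader might infer more than the documents support:

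- **That the SAP reports these patients as free of antibodies.** It never says so; that is only the everyday sense of the label.
- **That all early stoppers with ongoing antibodies are affected.** A lone positive at the last sample is already Indeterminate, and an unbroken run of 16 weeks or more is Persistent.
- **That patients stopping for toxicity are plainly affected.** The ADA note to Table 7 mentions EOS for toxicity, but the closing notes reserve EOS for progression or withdrawal of consent and send others to follow-up, where visit 7 may settle their status. Those notes need reconciling.
- **That follow-up visits 1, 4 and 7, each 12 weeks apart, create further cases.** The visit 4 ADA mark in protocol Table 9 carries a note limiting it to Group 6 patients who switch to SC dosing. The note's text names visit 3, but Table 8 confirms visit 4, which is the last visit for switchers who complete that schedule. Other patients are sampled at visits 1 and 7, 24 weeks apart, so two positives there are Persistent.
- **That the PK and AE assessments are distorted.** They use all treatment-emergent positives: "Possible relationship between AEs and treatment-emergent positive responses in the ADA assay will be assessed". The three-way split plays no part. Whether treatment-boosted patients should join that comparison, given that protocol 9.5.6 speaks of "the presence/absence of anti-cemiplimab antibodies", is a separate choice and not part of this point.

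**Conclusion.** The point holds as a wording defect with a limited effect. It mainly concerns Group 6 patients who stop for progression, are first positive at day 1 of cycle 3, 5 or 9, and are positive again at an EOS sample about 4 to 13 weeks later (EOS at 30 days, last dose no later than day 1 of the next cycle). They are counted as Transient when their status is unresolved, so Transient is overstated and Indeterminate understated by the same number.

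It would be wrong to conclude that persistent ADA is understated, because these patients have no documented 16-week run. Total treatment-emergent incidence and ORR are also unchanged. The number of patients depends on ADA incidence and discontinuation timing, which the documents do not give.

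The gaps assume nominal dosing days and an EOS sample counted by its actual date. SAP 5.10.2 counts by nominal time, and EOS has no nominal week, so the rule for that sample is itself unspecified.

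**What to change.** Reword two definitions in SAP 5.10.2 and leave Persistent as it is:

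- Indeterminate: treatment-emergent, not persistent, last collected sample positive, whatever the earlier pattern.
- Transient: treatment-emergent, not persistent, last collected sample negative.

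Add one sentence stating that the EOS sample uses its actual collection date for the 16-week count. Every treatment-emergent patient then falls into exactly one class. That includes a positive-negative-positive sequence ending on a positive, which moves from Transient to Indeterminate unless an earlier run already makes it Persistent. Carry the same rule into the separate ADA report that the SAP foresees.

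The cost is a few lines of SAP text and a small change to the derivation, with no new samples or visits. The downside is that more patients will be reported as Indeterminate, which is an honest description of what was observed.

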5.10.3. Analysis of Neutralizing Antibody (NAb) Data

The absolute occurrence (n) and percent of patients (%) with NAb status in the NAb analysis set will be provided by treatment groups.

5.10.4. Analysis of Exploratory Biomarker Data

Biomarker data will be analyzed using standard scientific methods and summarized by descriptive statistics and plots. Comparative analysis of biomarker data with parent study (R2810-ONC-1423) may be performed using paired t-test or nonparametric Wilcoxon signed-rank test or Chi-square test. Correlative analysis with clinical response may be performed using correlation coefficient, box plot and scatter plot, and basic regression models. Both comparative analysis and correlative analysis will be exploratory in nature and may be provided either as an appendix to CSR or in a separate report.

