1.1.1. Blockade of the PD-1 Checkpoint with Cemiplimab

Under chronic stimulation, T cells lose proliferative and effector function capacity, often due to signal down-modulation via the increased expression of proteins such as programmed cell death-1 (PD-1), an inhibitory checkpoint receptor of the CD28 receptor family. Blockade of the PD-1/PD-L1 T cell checkpoint pathway is an effective and well tolerated approach to stimulating the immune response, and has achieved significant objective responses in advanced melanoma, renal cell cancer (RCC), non-small-cell lung cancer (NSCLC), and other solid tumors (Postow 2015).

Cemiplimab is a high-affinity, human, hinge-stabilized IgG4P antibody directed to the PD1 receptor that potently blocks the interaction of PD-1 with its ligands, PD-L1 and PD-L2 (See the Investigator's Brochure for further details of nonclinical pharmacology and antitumor activity of cemiplimab). Cemiplimab was evaluated in the first-in-human (FIH) study R2810-ONC-1423 (NCT02383212). It was a phase 1, open-label, multicenter repeat dosing study of cemiplimab, alone and in combination with other anti-cancer therapies in patients with advanced malignancies and contains both dose escalation and expansion cohorts.

Additional Background for Amendment 6: Designs for new Groups 4 and 5 will encompass all advanced CSCC (defined as either metastatic [nodal or distant] CSCC or locally advanced CSCC that is not appropriate for surgery) as one entity.

Additional Background for Amendment 7: As was done in Groups 4 and 5, Group 6 will be open to all advanced CSCC patients. The intent of Group 6 is to provide additional efficacy and safety data for [REDACTED] IV for patients with advanced CSCC.

Additional Background for Amendment 9: Based on pilot experience in Group 5 (n=9), a single SC dose was shown to be well tolerated. The bioavailability of a single dose of cemiplimab SC was approximately 83% in Group 5 (Regeneron, data on file). Based on the desirability of improving patient convenience factors for treatment, and our initial experience in Group 5, it is appropriate to explore repeat doses of cemiplimab SC. Protocol Amendment 9 will offer approximately 18 patients in Group 6 who have completed ≥ 27 weeks of IV cemiplimab treatment (which corresponds to the first 3 tumor assessments on treatment) the option to receive subsequent doses [REDACTED]

Additional patients may be offered one of these options as available.

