4.2.2. Exclusion Criteria

A patient who meets any of the following criteria will be excluded from the study:

1. Ongoing or recent (within 5 years) evidence of significant autoimmune disease that required treatment with systemic immunosuppressive treatments, which may suggest risk for immune-related adverse events (irAEs). The following are not exclusionary: vitiligo, childhood asthma that has resolved, type 1 diabetes, residual hypothyroidism that required only hormone replacement, or psoriasis that does not require systemic treatment.
2. Prior treatment with an agent that blocks the PD-1/PD-L1 pathway.
3. Prior treatment with other immune modulating agents that was (a) within fewer than 4 weeks (28 days) prior to the first dose of cemiplimab, or (b) associated with immune-mediated adverse events that were \geq grade 1 within 90 days prior to the first dose of cemiplimab, or (c) associated with toxicity that resulted in discontinuation of the immune-modulating agent. Examples of immune modulating agents include therapeutic anti-cancer vaccines, cytokine treatments (other than G-CSF or erythropoietin), or agents that target cytotoxic T-lymphocyte antigen 4 (CTLA-4), 4-1BB (CD137), PI 3-K-delta, or OX-40.
4. Untreated brain metastasis(es) that may be considered active. (Note: patients with brain involvement of CSCC due to direct extension of invading tumor, rather than metastasis, may be allowed to enroll if they do not require greater than 10 mg prednisone daily, after discussion and approval of the medical monitor). Patients with previously treated brain metastases may participate provided that the lesion(s) is (are) stable (without evidence of progression for at least 6 weeks on imaging obtained in the screening period), and there is no evidence of new or enlarging brain metastases, and the patient does not require any immunosuppressive doses of systemic corticosteroids for management of brain metastasis(es) within 4 weeks of first dose of cemiplimab.

5. Immunosuppressive corticosteroid doses (>10 mg prednisone daily or equivalent) within 4 weeks prior to the first dose of cemiplimab.
Note: Patients who require brief course of steroids (eg, as prophylaxis for imaging studies due to hypersensitivity to contrast agents) are not excluded.
6. Active infection requiring therapy, including infection with human immunodeficiency virus, or active infection with hepatitis B virus (HBV) or hepatitis C virus (HCV).

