6.2.2. Follow-up

Patients who discontinue study treatment due to PD should return to the clinic 30 days (range: 21 to 42 days) after the last study treatment to complete the EOS assessments indicated in [Table 4](#) through [Table 9](#). After the EOS visit, patients should be followed for survival status until death, loss to follow-up, or study termination by the sponsor.

For all patients in Group 2, tumor biopsies ([Appendix 5](#)) should be obtained at time of progression, whether progression occurs in cycles 1 through 12 or during follow-up (after cycle 12).

Patients who discontinue study treatment due to reasons other than PD (eg, toxicity, confirmed CR after 48 weeks) should enter the follow-up schedule in [Table 9](#). (Note in clarification: Any patients who completed the posttreatment [Table 9](#) follow-up period of 6 months from previous amendments without disease progression will be asked to remain in follow-up. Such patients will be re-consented and asked to return approximately every 4 months (± 14 days) for 1 additional year to complete the extended follow-up assessments in [Table 9](#).)

For patients in Groups 1 or 2 who complete 12 cycles of treatment or for patients in Groups 3, 4, or 5 who complete 6 cycles of treatment without disease progression and subsequently experience disease progression during the follow-up period in [Table 9](#) without any intervening systemic anticancer therapy, resumption of treatment with cemiplimab 350 mg IV Q3W will be allowed. Prior to resumption of cemiplimab treatment, patients must be re-consented and repeat all screening activities (with the exception of providing new archived pathology material, or research biopsies), and the investigator must confirm that the patient still meets all eligibility criteria (other than the exclusion regarding prior treatment with anti-PD-1). Such patients will resume cemiplimab 350 mg IV Q3W for up to 108 weeks (maximum 12 retreatment cycles). The retreatment visit schedule will follow the study schedule in [Table 4](#). ADA samples will not be collected during retreatment. Patients in Group 5 who enter retreatment will not receive an additional dose of cemiplimab SC. For any patients who enter retreatment, the following are not required during retreatment: PK samples, research blood samples, and research tumor biopsies (exploratory tumor biopsies in Groups 2 and 4). *Note: Patients enrolled in Group 6 are not eligible for retreatment.*

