9.5.7. Analysis of Biomarker Data

Biomarker data will be analyzed using standard scientific methods and summarized by descriptive statistics and plot. Comparative analysis of biomarker data with parent study may be performed using paired t-test or nonparametric Wilcoxon signed rank test or Chi-square test. Correlative analysis with clinical response may be performed using correlation coefficient, box plot and scatter plot, and basic regression models. Both comparative analysis and correlative analysis will be exploratory in nature and will be described in a separate report.

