5.8.1. Analysis of Primary Efficacy Variable

The ORR according to central review will be summarized by group and the corresponding 2-sided 95% exact binomial confidence intervals will be derived using the Clopper Pearson method (Clopper, 1934). BOR will also be summarized by group.

The primary analysis of efficacy is based on the exact binomial confidence interval approach of ORR. If the lower limit of 95% confidence interval of observed ORRs excludes 15% for Group

1 and Group 3, excludes 25% for Group 2, exclude 20% for Group 4, or exclude 28% for Group 6, the study treatment is deemed effective for that group, respectively.

In addition, ORR along with two-sided 95% exact binomial confidence intervals for all patients treated with cemiplimab will be presented. ORR in patients whose CSCC disease has been confirmed by central pathology review will also be summarized.

A sensitivity analysis will be performed for ORR using patients who received at least one dose of cemiplimab.

For Group 6 patients who opt to switch to SC cemiplimab, efficacy data per central review will be censored at the first SC dose. Because Group 6 patients are only allowed to switch to SC cemiplimab after completing at least 27 weeks on study (3 tumor assessments after baseline), which is the pre-specified timepoint for primary efficacy analyses in Group 6, switching to SC dosing will have no impact on the primary efficacy analysis for Group 6.

The primary endpoint of ORR will also be summarized by pooling the objective response observed in CSCC patients in this study with object response data of CSCC patients in Regeneron study R2810-ONC-1423 to satisfy regulatory requirements from certain regions. Details will be provided in separate SAP for integrated efficacy analysis.

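### Paired tests are named for comparing biomarkers with study R2810-ONC-1423, but the two studies' samples are independent, so the paired t-test and signed-rank test do not apply

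*SAP*

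**What the plan says.** SAP section 5.10.4 describes a comparison between this trial and another one: "Comparative analysis of biomarker data with parent study (R2810-ONC-1423) may be performed using paired t-test". In full, the comparison "may be performed using paired t-test or nonparametric Wilcoxon signed-rank test or Chi-square test". Protocol section 9.5.7 has the same sentence without the study number: "Comparative analysis of biomarker data with parent study may be performed using paired t-test or nonparametric Wilcoxon signed rank test or Chi-square test". Both sections allow the analysis rather than require it, and both label it exploratory.

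Four other places bear on whether pairs can exist:

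- Protocol section 1.1.1 says of R2810-ONC-1423: "It was a phase 1, open-label, multicenter repeat dosing study of cemiplimab, alone and in combination with other anti-cancer therapies".
- Protocol section 4.2.2, exclusion criterion 2, reads: "Prior treatment with an agent that blocks the PD-1/PD-L1 pathway".
- Protocol section 6.2.2 relaxes that criterion once, for retreatment of this trial's own Groups 1 to 5 patients, who must meet all eligibility criteria "other than the exclusion regarding prior treatment with anti-PD-1".
- SAP section 5.8.1 plans a summary of ORR by "pooling the objective response observed in CSCC patients in this study with object response data of CSCC patients in Regeneron study R2810-ONC-1423", which treats the two studies as separate sets of patients.

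**The concern.** A paired t-test and a signed-rank test both work on differences within a pair: the same patient measured twice, or two patients matched by a stated rule. For continuous biomarkers these are the only tests the two sections name, and the comparison they are attached to is between studies. If the studies share no patients and no matching rule exists, there are no differences to analyse. An analyst following the text would have to invent a pairing or depart from the plan. What is at stake is the definition and efficiency of an optional between-study biomarker comparison, and whether the SAP sentence can be carried out as written.

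**Working it through.** No figure in the documents depends on this point, so the main check is one of logic, followed by an illustration.

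**1. Can one patient be in both studies?** Every regimen that protocol section 1.1.1 describes for R2810-ONC-1423 contains cemiplimab, a PD-1 blocker. Exclusion criterion 2 bars prior treatment of that kind and gives no waiver at first enrolment. The single relaxation, in section 6.2.2, concerns patients already enrolled here. A patient treated in R2810-ONC-1423 therefore cannot enter this trial.

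**2. Is there matching between different patients?** None is defined in the visible text of either document.

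**3. Which of the named tests fit independent samples?**

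| Test | Needs pairs? | Fits the between-study comparison? |
|---|---|---|
| Paired t-test | Yes | No |
| Wilcoxon signed-rank | Yes | No |
| Chi-square | No | Yes, for categorical markers |

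**4. What would forced pairing cost?** Take independent samples of sizes n1 and n2 with common SD 1, and let m be the smaller size. The standard error of the mean difference is √(2/m) after arbitrary pairing and √(1/n1 + 1/n2) when all patients are used. The following are assumptions, not document figures: this trial n1 = 60; other study n2 = 60, 26 or 15; true shift 0.6 SD; two-sided alpha 0.05; normal data; 4,000 simulated trials per row. The value 60 equals the largest biopsy count in protocol Table 14.

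| n1, n2 | Patients dropped (n1 + n2 − 2m) | SE, forced pairs | SE, all patients | Power, forced pairs | Power, Welch | Type I error, forced pairs |
|---|---|---|---|---|---|---|
| 60, 60 | 0 | √(2/60) = 0.183 | 0.183 | 0.89 | 0.90 | 0.056 |
| 60, 26 | 34 | √(2/26) = 0.277 | √(1/60 + 1/26) = 0.235 | 0.55 | 0.71 | 0.054 |
| 60, 15 | 45 | √(2/15) = 0.365 | √(1/60 + 1/15) = 0.289 | 0.33 | 0.52 | 0.054 |

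The simulation error on a type I rate near 0.05 is √(0.05 × 0.95 / 4,000) = 0.003, so the last column is close to nominal.

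**5. How much does the pairing itself matter?** On one simulated data set of 60 and 26 patients, 5,000 random pairings gave paired p-values from about 0.001 to 0.38 (central 95%; median 0.045). Welch's test on the same data gives a single value, 0.011.

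**6. Does any stated power figure move?** The biomarker powers in protocol Table 14 use a one-sided Chi-square test at 20% type I error. The formula is Φ[(p2 − p1 − 0.8416·SE0)/SE1], with SE0 pooled and SE1 unpooled. For 30 against 30 patients and 10% against 30%, SE0 = √(0.2 × 0.8 × 2/30) = 0.1033 and SE1 = √((0.09 + 0.21)/30) = 0.1. Power = Φ[(0.2 − 0.0869)/0.1] = Φ(1.131) = 87.1%, against 87% stated. All 12 entries reproduce within one percentage point. None uses a paired test, so none changes.

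**The case against.** The strongest reply is that the sentence compresses two analyses. Inclusion criterion 14 requires Group 2 and 4 biopsies at baseline, cycle 1 day 29 and progression, and paired tests are right for changes between those samples. The authors may have meant paired tests within patients and Chi-square between studies. This is plausible, and a reader should not infer a deliberate plan to pair different patients. But the text attaches all three tests to the other study, so the reply explains the fault without curing it.

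Second, a reader might infer that every test named is invalid. The documents do not support that: the Chi-square test in the same sentence suits categorical markers in independent samples.

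Third, a reader might infer that the resulting p-values would be meaningless or too small. The simulation does not bear this out: when pairing ignores the data, type I error stays near nominal. The harm is an arbitrary result and lost data, and the power loss almost disappears when the samples are equal in size.

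Fourth, several biomarker and exploratory sections are blacked out, so a matching rule could exist out of sight. That stands as a limit on the statement about matching. It does not restore same-patient pairs, which eligibility rules out.

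Finally, the comparison is optional and exploratory and may never be done. That lowers the weight of the point but does not make a paired test applicable to unpaired data.

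**Conclusion.** The point holds for the paired t-test and the Wilcoxon signed-rank test when used to compare biomarkers with R2810-ONC-1423. The samples are independent on the visible text, and the two tests could be run only after an arbitrary pairing that the plan does not specify.

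The consequence is small. It concerns one optional, exploratory comparison of continuous markers. No primary endpoint, alpha, sample size or Table 14 power figure is touched. The sizes above (34 patients dropped and power of 0.55 against 0.71 at 60 and 26) rest on assumed sample sizes and an assumed shift of 0.6 SD; they show direction and order of magnitude, not this trial's actual loss.

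Two assumptions remain. No matching rule sits in redacted text. And treatment in R2810-ONC-1423 came first, as calling it the parent study implies; exclusion criterion 2 says nothing about patients who might move in the other direction.

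**What to change.** Rewrite the sentence in SAP section 5.10.4 as two:

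- Between this trial and R2810-ONC-1423: a two-sample (Welch) t-test or Wilcoxon rank-sum test for continuous markers, and the Chi-square test for categorical markers.
- Within patients of this trial, such as baseline against cycle 1 day 29 biopsies: a paired t-test or Wilcoxon signed-rank test.

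Make the same change in protocol section 9.5.7. Until the protocol is next amended, the difference can be recorded in SAP section 1.2.4, which already lists departures from the protocol's statistical section.

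As an option only, the between-study comparison could take account of metastatic versus locally advanced disease. That would need a regression model or a stratified rank test, because neither a Welch nor a rank-sum test takes a covariate.

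The cost is wording. No new data, patients, assays or recalculation are needed.
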